Baseline: Participants sign on to Zoom via the link provided during their assigned timeslot. Upon signing into the Zoom meeting, the research assistants provide a link (using the chat function) directing them to a Qualtrics survey. Participants read and view videos of the study procedures on the first page of this website. The videos have been created in Powtoon, using voiceover and images that are not related to a specific gender or race/ethnicity. After reviewing the videos, participants are provided with the informed consent document (on a subsequent page of the survey), will have the opportunity to ask questions during the live Zoom session with the research assistant. After consenting to participate, they are directed to complete the baseline survey (approximately 30-45 minutes). All participants will complete this computerized survey that assesses alcohol use, alcohol-related problems, protective behavioral strategies for drinking and their perceived effectiveness, motives and expectancies for alcohol use, anonymized social network characteristics, context of their most recent drinking occasion, marijuana and tobacco use, COVID-19 experiences, internalizing symptoms, and demographic

measures. Through a mechanism of the survey, participants are randomly assigned to one of six possible conditions regarding the timing of receiving emailed personalized feedback about their alcohol use. After completing the initial assessment, participants are then be directed to navigate through the eCHECKUP TO GO program (San Diego State University Research Foundation, 2018) until it is completed (approximately 20-30 minutes).

Subsequent assessments: Approximately 1, 3, 6, and 9 months after the initial assessment, researchers send each participant an email reminding them to complete the follow-up assessment. This email includes a link to an online follow-up survey that assesses alcohol use, related problems, protective behavioral strategies for drinking and their perceived effectiveness, anonymized social network characteristics, context of their most recent drinking occasion, and marijuana and tobacco use. If participants provide additional ways to contact them during the baseline survey (a second email address, a phone number to text), these methods are also used to send the link to the follow-up surveys.

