Statistical Analysis Plan

Timing Personalized Feedback After Alcohol Health Education (TIME)

NCT04453007

11/13/2020

Statistical Analysis Plan

Prior to hypothesis testing, the data will be examined for normality and outliers. Histograms and values for skewness and kurtosis will be examined. Positively skewed variables will be natural log transformed, unless paired with an excessive number of zeroes. If there are an excess of zeroes in an outcome, the variable will be dichotomized if other values are not well represented, or appropriate modeling techniques will be used (e.g., hurdle models) if other values are well represented. Boxplots will be used to check for outliers. Extreme values will be winsorized (i.e., cases retained in the sample, but values made less extreme). Cases with missing data will be compared to complete cases across major study variables to identify if there are systematic differences in missingness. If significant associations are identified, these variables will be used as covariates in later analyses.

To address the major aim of the study, the data will be analyzed using latent growth models within a structural equation modeling framework. Separate models will be conducted for each alcohol outcome: alcohol consumption (e.g., quantity), and alcohol-related problems. It is not known the exact trajectory across time (baseline, 1 month, 3 months, 6 months, 9 months), so a few models will be compared to identify which best captures the shape of change over time. A simple model that reflects change to 1 month (slope 1; initial change post-intervention) and longer-term maintenance (slope 2; linear growth to 9 months) will be compared to models with additional piecewise slopes or curvilinear components in case longer-term maintenance is not a linear process. Study condition (6 groups) will be dummy coded across 5 variables with “no booster” as the category of reference, and will serve as a predictor of each latent variable (latent intercept, each slope). All models will be conducted using maximum likelihood estimation, and will control for gender. The model for problems will also control for alcohol quantity.

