Given prior findings that emailed booster feedback containing personalized normative feedback and protective behavioral strategies (PBS) was significantly more effective for select groups (i.e., those lower in PBS use [Braitman & Henson, 2016], legal age drinkers [Braitman & Lau-Barraco, 2018]), we will examine potential moderators of booster efficacy as a supplementary exploratory analysis. Legal drinking status by age (coded as 1 = *age 21-24* [legal], 0 = *age 18-20* [underage]) and baseline PBS use (in its original continuous metric) will be explored as potential moderators. For each outcome, two additional models will be conducted (one for each moderator). The moderator will be added as a predictor of each latent factor (latent intercept, slope 1, and slope 2). Multiple interaction terms will be created to capture the interaction with condition (dummy coded across 5 variables). These interaction terms will also be included as predictors of each latent factor. Thus, the outcome at baseline and change over time will be predicted by condition, the moderator, and the interaction between the two, controlling for relevant covariates.

References:

- Braitman, A. L., & Henson, J. M. (2016). Personalized boosters for a computerized intervention targeting college drinking: The influence of protective behavioral strategies. *Journal of American College Health, 64*(7), 509-519.
<http://doi.org/10.1080/07448481.2016.1185725>
- Braitman, A. L., & Lau-Barraco, C. (2018). Personalized boosters after a computerized intervention targeting college drinking: A randomized controlled trial. *Alcoholism: Clinical and Experimental Research, 42*(9), 1735-1747.
<http://doi.org/10.1111/acer.13815>

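### Baseline strategy use and legal-age status, which the SAP ties to booster response, are not prespecified covariates in the main models; adding them is a modest precision gain

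*SAP*

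**What the plan says.** The SAP's main-analysis paragraph sets the covariates for the growth models:

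- For both outcomes: "All models will be conducted using maximum likelihood estimation, and will control for gender".
- For the second outcome there is one addition: "The model for problems will also control for alcohol quantity".
- After comparing cases with missing data to complete cases on major study variables: "If significant associations are identified, these variables will be used as covariates in later analyses".
- Baseline is one of the five modelled time points. Study condition, as five dummies against no booster, "will serve as a predictor of each latent variable (latent intercept, each slope").

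The SAP's moderator paragraph reports that in prior work the emailed booster "was significantly more effective for select groups", namely those lower in PBS use and legal-age drinkers. It then says "we will examine potential moderators of booster efficacy as a supplementary exploratory analysis". Legal drinking status and "baseline PBS use (in its original continuous metric) will be explored as potential moderators". Each gets its own model per outcome, with a main effect on every latent factor and interactions with the five condition dummies.

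The protocol confirms that PBS use is in the baseline survey (Study Procedure, Baseline) and that age is recorded at the initial assessment (Measures). On allocation it says "Through a mechanism of the survey, participants are randomly assigned to one of six possible conditions". It mentions no stratification.

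**The concern.** The SAP gives a reason to think that PBS use and legal-age status matter for how drinking changes after a booster, and both are in hand before any booster is sent. The main models nevertheless fix gender as the only covariate common to both outcomes, and no reason is given for leaving the other two out. The missingness rule might bring either one in, but only if the observed data happen to trigger it.

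Two things are at stake. Any slope variance that these variables explain stays in the residual. In addition, the aim is to rank delivery times using small arms, so a chance difference in age mix or strategy use between arms is carried unadjusted into the comparison of timings.

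**Working it through.** **Inputs.** From the protocol: N = 180, six conditions, 76% expected retention, b = 6.57, β = 0.537, power .80+. Assumed: equal allocation (the ratio is not stated), a legal-age share of 40% to 60%, two-sided α of 0.05, and the share R² of residual slope variance explained by the two covariates. The documents give no figure for the legal-age share or for R².

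**The plan's own figure.** The power statement cannot be confirmed or refuted. The variances, covariances, α, target parameter and type of standardisation are not given. A simple two-means approximation, with β read as a difference in SD units, gives these results:

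- one booster arm against control (180 × 0.76 / 6 = 22.8 retained per arm): power 0.442
- all booster arms pooled against control: 0.648
- two groups of 68.4: 0.881

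If β is instead fully standardised on a one-in-six dummy, d = 0.537 / √(1/6 × 5/6) = 1.44, and power for one booster arm against control is 0.998. Some readings meet .80 and others do not. The figures below therefore do not depend on it, except where power is named.

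**Chance imbalance.**

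1. Arm size: 180 / 6 = 30.
2. The SD of the difference in legal-age share between two arms is √(2p(1−p)/30). At p = 0.5 this is 0.129. At p = 0.4 or 0.6 it is 0.126. That is about 13 points.
3. A gap of 20 points is 6 people out of 30. With six independent binomial(30, p) counts, P(at least one booster arm differs from control by 6 or more) = 1 − Σ P(control = c) × P(a booster arm is within 5 of c)^5. At p = 0.5 this is 0.472. At p = 0.4 or 0.6 it is 0.451. If arm sizes also vary at random, it is about 0.40.

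**What such an imbalance could do.** Suppose legal age alone explained a share R² of slope variance at p = 0.5. Its coefficient would be √R² / 0.5 slope SDs, and a 20-point gap would move a contrast by 0.2 × √R² / 0.5. That is 0.06 SD at R² = 0.02 and 0.13 SD at R² = 0.10. For comparison, the standard error of a contrast between two arms of 30, in the same units, is about √(2/30) = 0.26.

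**Precision gain.** Sample-size equivalent = 180 × (1/(1−R²) − 1). Fall in standard error = 1 − √(1−R²). Power is for one booster arm against control with β in SD units, where the unadjusted value is 0.442.

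| Assumed R² | Extra participants out of 180 | Fall in SE | Power |
|---|---|---|---|
| 0.02 | 3.7 | 1.0% | 0.449 |
| 0.05 | 9.5 | 2.5% | 0.460 |
| 0.10 | 20.0 | 5.1% | 0.481 |

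**Is there reason to expect R² above zero?** Let γ be a moderator's association with slope among controls, and δ the average change in that association once a booster has been sent. With equal arms, the pooled association within arms is γ + (5/6)δ over a period when all five booster arms have been sent one. By 1 month only the 2-week arm and the repeated-delivery arm have been, so for the first slope it is about γ + (2/6)δ. If δ is not zero, as the SAP's cited findings suggest, the pooled association vanishes only when γ happens to cancel it.

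**The case against.** The strongest reply is that the SAP names these variables as moderators, not as prognostic factors. A moderator need not predict change in drinking, a main effect does not model differing booster response, and the SAP already plans the interactions. This stands in part. Main-effect adjustment is no substitute for the moderator models, and the documents do not show how much precision it would buy. But because five of the six arms receive boosters, an effect modifier would normally show some association with slope in the pooled sample, though less for the first slope.

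Second, baseline drinking is itself modelled and condition predicts the intercept, so an imbalance that affects only the starting level is carried there. This stands: only the covariates' association with slope matters for the timing contrasts.

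Third, a prespecified gender adjustment with separate exploratory moderation is a legitimate choice. That also stands, and it is why this is an improvement and not an error.

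A reader might infer more than the documents support:

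- *That the main models adjust for gender alone.* They do not: the problems model adds alcohol quantity, and the missingness rule can add others, possibly including PBS use or age.
- *That the contrasts are biased.* Under randomisation the omission causes no systematic bias.
- *That the trial is underpowered.* The inputs to the power simulation are not given, so this cannot be judged here.

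**Conclusion.** The point holds as a minor efficiency improvement. Gender is the only prespecified covariate common to both main models. PBS use and legal-age status are collected, are cited by the SAP as related to booster response, and appear only in the exploratory models.

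A sizeable chance gap in age mix between control and some booster arm is close to an even chance (about 47% for 20 points or more at a 50% share with 30 per arm). Its likely effect on a contrast is nonetheless small next to the standard error. The precision gain is also modest, and could be close to nothing if the covariates turn out to be weakly related to slope. All sizes rest on equal allocation, an assumed legal-age share and an assumed R².

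**What to change.** Add one sentence to the SAP's main-analysis paragraph, for example:

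> In both main models, baseline PBS use (mean-centred) and legal drinking status (1 = age 21-24, 0 = age 18-20) will be included with gender as predictors of the latent intercept and of every slope, and will be retained whatever their p-values.

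Keep the condition-by-moderator interactions as exploratory. If the sponsor prefers to leave the two variables out, a sentence giving the reason would do. If outcomes by condition have already been examined, report the adjusted models as a labelled sensitivity analysis.

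The cost is small, and no new data are needed. With an intercept and two slopes, two covariates add 2 × 3 = 6 paths per model, on top of the (5 + 1) × 3 = 18 for the condition dummies and gender. That is a real, though limited, burden in a growth model of this size, and it buys little if the covariates are weak. Prespecifying them also takes their inclusion out of the hands of the missingness screen. If they predict dropout, it makes the missing-at-random assumption behind maximum likelihood more plausible.
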